### 3.0 DESIGN

This protocol amendment includes participant follow-up only. Study enrollment has been closed since 15 Oct 2008 and no new study participants will be enrolled. Data collection will only take place if a participant requires a secondary procedure/reoperation. There are no longer requirements for scheduled office visits or annual participant questionnaires. The study is currently in year 7 and follow-up will continue through 10 years or until the National Breast Implant Registry opens for data collection, whichever occurs first.

As in the original protocol, there will be no concurrent controls needed as a source of comparison for secondary procedures/reoperations (see local complications category in original study design Tables 1 and 2). Thus, saline implant participants will not have data collected under this amended protocol.

Mentor will employ third party study entities that will be responsible for the following: (1) collecting data from surgeons; (2) entering data into and administering the study database; (3) generating follow-up reports as well as datasets; (4) meeting with Mentor on a regular basis; and (5) analyzing the study data. Mentor will be responsible for: (1) IRB approval; (2) monitoring third party entities; (3) analyzing the study data; and (4) periodic reporting to FDA.

The postapproval study was originally designed as follows:

*MemoryGel™ PAS uses a current cohort design of the first 41,900 women receiving Mentor's MemoryGel implants, with 10 years of follow-up. It will include augmentation, reconstruction, and revision patients, each in their naturally occurring proportions at participating study sites.*

*For the purpose of assessing rheumatological and neurological signs and symptoms, there also will be 1,000 saline breast implant patients from the participating surgeons' practices who will serve as concurrent controls. Concurrent control participants will be enrolled by approximately 30 physicians who routinely use saline implants. These investigative sites will be selected with the objective of obtaining the desired number of controls in an appropriate time frame, e.g. roughly the same time frame as the recruitment of MemoryGel subjects. These sites are to enroll all saline subjects meeting the specified eligibility criteria until 1,000 controls are recruited into this study.*

*Women will be enrolled into the postapproval study consistent with the flow chart in Figure 1. Baseline data will be collected from the participant using survey methodology. Limited data on operative characteristics will be collected from the surgeon. Follow-up data will be collected from the participant by a combination of mail, Internet, and telephone survey methodologies annually from 1–10 years, and on an interim/unscheduled basis, as needed, for key local complications and results of MRI evaluations (MemoryGel patients only), and results from rheumatological or neurological referral evaluations (MemoryGel and saline patients). Additionally, the surgeon will see the MemoryGel participants at year 1, a second time during years 4–6, a third time during years 9–10, and at unscheduled/interim visits. All local complications, including reasons for reoperation, with or without removal, and reasons for removal, reported by the participant or diagnosed by the surgeon will be recorded during these visits.*

*Controls for the postapproval study, including the concurrent controls, are indicated in Table 2.*

*Mentor will employ third party study entities that will be responsible for: (1) tracking participants throughout the 10-year study period; (2) collecting the baseline and follow-up questionnaire data and interim local complication forms from participants; (3) collecting data from surgeons; (4) entering data into and administering the study database; (4) generating enrollment and follow-up reports as well as datasets; (5) meeting with Mentor on a regular basis; and (6) analyzing the study data. Mentor will be responsible for: (1) physician enrollment; (2) IRB approval; (3) monitoring the third party entities; (4) study initiation; and (5) periodic reporting to FDA.*

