## 1.0 INTRODUCTION

On 17 Nov 2006, the U.S. Food and Drug Administration (FDA) approved Mentor's MemoryGel® silicone gel-filled breast implants for use in women who are undergoing primary or revisional breast augmentation and primary or revisional breast reconstruction surgery. The approval was conditional on Mentor conducting a 10-year study designed to collect long-term experience in U.S. women with MemoryGel implants. The MemoryGel Postapproval Study (MemoryGel PAS) is intended to satisfy one element of FDA's postapproval requirements.

As a condition to gaining access to MemoryGel products, physicians were required to sign up for the MemoryGel Gel-Filled Breast implants Post Approval study, and were asked to actively encourage 41,900 women to participate in the 10-year study. In addition, the study included 1,000 women who were undergoing breast implantation with saline breast implants to serve as concurrent controls for assessing rheumatologic and neurologic signs and symptoms.

Approximately 1,700 centers participated in the study and enrollment included 41,451 MemoryGel participants and 1039 saline participants. Study enrollment has been closed since 15 Oct 2008. As of the last annual study report (dated Nov 2013), the follow-up rates through six years were 21.8% for MemoryGel participants and 15.0% for saline participants.

Due in part to the low follow-up rate, which may limit interpretation of the data, FDA in collaboration with the American Society of Plastic Surgeons (ASPS), breast implant manufacturers, and patient representatives have been investigating innovative approaches to collect long-term data on silicone gel breast implants. As part of these efforts, recently, FDA has agreed to changes in the postapproval commitments for the MemoryGel silicone gel-filled breast implants that include changes to MemoryGel PAS. These changes are described in this amended protocol.

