**Rheumatological and Neurological Signs and Symptoms**

*In contrast to all of the above analyses, this analysis will be based on both the MemoryGel participants and the concurrent saline controls. The study will collect information on rheumatological and neurological signs and symptoms.*

*For each individual rheumatological and neurological sign and symptom, the rheumatological categories for persistent fatigue, combined pain, and fibromyalgia-like symptoms, and the combined neurological categories for central nervous system-related, peripheral nervous system-related, and muscle-related signs and symptoms, the post-baseline prevalence will be estimated for each participant as the proportion of post-baseline contacts in which the participant reports the sign or symptom to be present at the time of the contact. These proportions will be averaged across MemoryGel participants and averaged across the controls. For all of the above, except the individual signs and symptoms, the proportions for the control participants will be compared to the corresponding proportions for the approximately 10,000 MemoryGel participants with whom they are concurrent. Regression analyses will be used to adjust for differences in age, race, and other relevant patient characteristics. The significance of the difference between the two will be tested for significance using a one-sided test conducted at the 0.05 level of significance. These means will be compared using a test based on the normal approximation. In addition, 95% confidence intervals for the estimated prevalences will be computed.*

*These analyses will be performed for the following rheumatological signs and symptoms categories:*

- *Persistent fatigue*
- *Combined pain*
  - *persistent non-traumatic joint pain (more than 3 months), **OR***
  - *persistent muscle pain (more than 3 months), **OR***
  - *pain in taking a deep breath for more than a few days (pleurisy)*
- *Fibromyalgia-like symptoms*
  - *VAS fatigue scale  $\geq 6$  **AND***
  - *Regional pain scale (RPS)-derived body pain questionnaire  $\geq 8$*

*Additionally, these analyses will be performed for the following combined neurological categories:*

- *Central nervous system (CNS)-related*
  - *persistent memory problems and difficulty concentrating on simple tasks, such as reading or television lasting at least 3 months, **OR***
  - *seizure, convulsion, or fit **OR***
  - *episode of sudden visual loss or double vision, **OR***

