## 11.2 Sample Size Determination

Study enrollment has been closed since 15 Oct 2008 and no new study participants will be enrolled.

The sample size for the postapproval study originally was determined in the following manner:

*It is assumed that it is required to have 80% power to be able to detect as statistically significant a relative risk of 2.0 for adverse events that occur, without implants, with a frequency of 2.85 per 100,000. This figure is based on the incidence of scleroderma as reported by Mayes et al. (2003). It is assumed this would be based on a one-sided test conducted at the  $\alpha = 0.05$  level of significance. Based on these specifications, it was determined that approximately 338,000 person-years would be required.*

*Patients are to be followed for 10 years. For purposes of sample size calculation, assuming a follow-up rate of 65% at 10 years and a linear loss to follow-up, there would be an average of 8.075 person-years per participant. Thus, in order to obtain the 338,000 person-years, a total of 41,900 MemoryGel participants would be required.*

*The concurrent control sample size was selected in order to be able to detect a relative risk of 2.0 for MemoryGel participants as compared to control participants, for rheumatologic and neurologic signs and symptoms with a prevalence of approximately 2% among MemoryGel participants. It is assumed this would be based on a one-sided test conducted at the 0.05 level of significance with a power of 80%. Similar combined rheumatologic categories of signs and symptoms from Mentor's existing Core Study of these silicone gel implants all have estimated prevalence of at least 2% after year 2. These data will be analyzed by first computing, for each participant, the proportion of time points in which the participant reports the sign or symptom as being prevalent and then calculating the mean of these participant-level proportions across participants within each group. For purposes of sample size calculation, it is assumed that these means will be compared using a simple test based on the normal approximation.*

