*Given an expected 65% follow-up rate at 10 years, it is assumed participants will have reports, on average, at 8 time points. The correlation between different reporting time points for an individual participant is taken into account. From Mentor's existing Core Study of silicone gel-filled breast implants, for the three combined categories of signs and symptoms correlations between time points that are 1 year apart range from 0.47 to 0.59, and correlations between time points that are 2 years apart range from 0.35 to 0.41. As expected, the correlations decrease with distance between time points. On average, considering all pairs of time points and ignoring loss to follow-up, time points will be 3.7 years apart. (For example, years 1 and 3 are 2 years apart and years 1 and 10 are 9 years apart.) Thus, it is assumed that the correlation, on average, would not be higher than 0.30. Based on the above, it was determined that a sample size of 1,000 concurrent controls would be more than sufficient.*

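### The saline controls were planned to come from about 30 physicians, but the signs-and-symptoms test makes no stated allowance for correlation within a practice; any that remains after adjustment makes the one-sided test liberal and the saline interval too narrow.

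*Combined protocol and SAP*

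**What the plan says.** All locations are in the combined protocol and SAP.

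- **Source of the controls (Section 3.0).** "Concurrent control participants will be enrolled by approximately 30 physicians who routinely use saline implants". Recruitment within a practice is exhaustive: "These sites are to enroll all saline subjects meeting the specified eligibility criteria until 1,000 controls are recruited into this study". The number of physicians who actually enrolled saline women is not reported.
- **Size of the study (Section 1.0).** "Approximately 1,700 centers participated in the study and enrollment included 41,451 MemoryGel participants and 1039 saline participants".
- **Analysis (Section 11.1, Rheumatological and Neurological Signs and Symptoms).** Each woman's proportion of positive reports is averaged within group. The controls are set against the "approximately 10,000 MemoryGel participants with whom they are concurrent". Regression is to adjust for age, race and other patient characteristics, and the difference is tested one-sided at 0.05. "These means will be compared using a test based on the normal approximation". Ninety-five percent intervals are given for the prevalences.
- **Sample size (Section 11.2).** The calculation allows for correlation between time points within a woman and concludes that "a sample size of 1,000 concurrent controls would be more than sufficient". It mentions no correlation between women of the same physician.
- **Status.** Amendment 2 collects no saline data (Section 3.0). The Complications/Reoperations text in Section 11.1 still requires a final report on the Amendment 1 phase, analysed as in the original protocol.

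**The concern.** Taking every eligible saline patient from a small set of practices is cluster sampling. Women of one practice may share region, referral pattern and mix of augmentation, reconstruction and revision. If their symptom proportions are correlated, the effective number of controls is below 1,039.

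The saline group is the smaller one and supplies most of the variance of the difference, so an error in its variance passes almost fully into the test. The planners allowed for correlation within a woman but not at the level above her. No section mentions a site effect, a random effect, a cluster-robust variance or an ICC.

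At stake are the error rate of each of six one-sided tests (three rheumatological and three neurological categories) and the coverage of the saline intervals. The risk is that a symptom difference is declared, or an interval looks precise, on a standard error that is too small.

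**Working it through.** **1. The plan's own figure.** Inputs from Section 11.2: 2% prevalence in MemoryGel women and relative risk 2.0, hence 1% in controls; one-sided 0.05; 80% power; 8 reports per woman; correlation 0.30. The allocation of about 10:1 follows from Section 11.1.

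- Pooled two-proportion formula: n = [z_α √(p̄(1−p̄)(1+1/k)) + z_β √(p₁(1−p₁)+p₂(1−p₂)/k)]² / (p₂−p₁)²
- With p₁ = 0.01, p₂ = 0.02, k = 10 and p̄ = 0.0191, n is about 1,074.
- Repeated-report factor: (1 + 7 × 0.30)/8 = 0.3875.
- Controls needed: 1,074 × 0.3875 = 416.2, so 417.

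Power with 1,000 v 10,000 is 99.4%. The statement that 1,000 is ample therefore reproduces, if women are independent of each other.

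**2. Clustering at full enrolment.** Women per cluster: 1,039/30 = 34.6 for controls. For MemoryGel, 10,000/1,700 = 5.9, which assumes that the concurrent women are spread over all centers. The ICC is that of the participant-level proportion and is assumed.

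- Design effect: DE = 1 + (m − 1) × ICC
- True/naive SE: r = √[(DE_c/1,039 + DE_m/10,000) / (1/1,039 + 1/10,000)]
- True one-sided alpha: 1 − Φ(1.645/r)
- Shortfall of the naive SE: 1 − 1/r
- Coverage of the nominal 95% saline interval: 2Φ(1.96/√DE_c) − 1

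Prevalence and the factor 0.3875 cancel from r when the groups are equal. Controls supply (1/1,039)/(1/1,039 + 1/10,000) = 91% of the naive variance.

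Example, ICC 0.01: DE_c = 1 + 33.6 × 0.01 = 1.34; DE_m = 1.05; r = 1.144; alpha = 1 − Φ(1.438) = 7.5%.

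| Assumed ICC | Control DE | r | Naive SE too small by | True alpha | Saline interval coverage |
|---|---|---|---|---|---|
| 0.001 | 1.03 | 1.015 | 1% | 5.3% | 94.6% |
| 0.005 | 1.17 | 1.07 | 7% | 6.3% | 93% |
| 0.01 | 1.34 | 1.14 | 13% | 7.5% | 91% |
| 0.02 | 1.67 | 1.27 | 21% | 9.8% | 87% |
| 0.05 | 2.68 | 1.60 | 37% | 15.1% | 77% |

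**3. Sensitivity to the cluster-size inputs.** With 24.4 MemoryGel women per center (41,451/1,700) in place of 5.9, alpha at ICC 0.05 is 15.5% rather than 15.1%. Unequal cluster sizes raise the figures: with 1,000 controls and an assumed coefficient of variation of 0.6, alpha at ICC 0.01 is 8.2%, against 7.4% with equal clusters.

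**4. Attrition.** Saline follow-up through six years was 15.0% (Section 1.0): 0.150 × 1,039 = about 156 women, or 5.2 per physician. The same formulas with 156 v 10,000 give alpha of 5.2%, 5.4%, 5.7% and about 6.7% at ICC 0.005, 0.01, 0.02 and 0.05. Women who reported only in earlier years also enter the averages, so the analysis lies between steps 2 and 4.

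**5. Power of a clustered test.** With 1,039 v 10,000 women, 2% v 1% and a pooled variance, power is about 98% at ICC 0.01, 94% at 0.02 and 80% at 0.05. With an unpooled variance it is about 92% at 0.05.

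**The case against.** **The ICC may be negligible.** Symptoms are reported by the women themselves, by mail, Internet or telephone, and are not rated by the surgeon. There is no shared rater, and at ICC 0.001 alpha is essentially nominal. This stands as a limit on size. It does not change the direction, and the plan gives no estimate that would settle it.

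**Covariate adjustment handles the mechanism.** Case mix and indication are patient characteristics and may be covered by the planned regression. This also stands in part: only the residual correlation matters, and the table makes no allowance for adjustment. The plan does not say how the regression standard errors are obtained, so independence between women is inferred from the named test and from silence on clustering.

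**Physician effects cancel.** They would if the MemoryGel comparators came from the same physicians in proportion; the naive test would then be slightly conservative. At the average of 24.4 women per center, however, 30 centers supply about 730 of the 10,000, so little cancels. The documents do not say which centers the 10,000 came from.

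**Low follow-up matters more.** It shrinks the clusters, as step 4 shows, and 15.0% saline follow-up is a larger threat to validity than a modest design effect. Both can be true; the variance is the cheaper one to repair.

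A reader might go further and infer three things that the documents do not support:

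- That the test is shown to be too liberal. Without an ICC, this is conditional.
- That 1,000 controls were too few. A clustered test keeps about 80% power even at ICC 0.05 with full enrolment.
- That this is the only use of the saline women. Section 11.1 also lists them as a comparison source for fibromyalgia.

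**Conclusion.** The point holds as a conditional weakness that is cheap to correct. If any positive site-level correlation remains after adjustment, the stated test exceeds its nominal 5% and the saline 95% interval undercovers. At full enrolment the true alpha runs from 5.3% to 15.1% for assumed ICCs of 0.001 to 0.05. If only late reporters contribute, it is about 5.2% to 6.7% for 0.005 to 0.05.

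These figures rest on three assumptions: the ICC range, the planned number of about 30 physicians, and roughly equal cluster sizes. The harm is mainly to error rate and coverage, not to power. It concerns the Amendment 1 final report only. A reader might extend it to the Amendment 2 reoperation analysis, but that analysis has no saline comparison.

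**What to change.** In the Amendment 1 final report:

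- Base the signs-and-symptoms test and the 95% intervals on site-level cluster-robust standard errors, with a small-sample correction for the number of saline sites, or fit a random site effect in the planned regression.
- Report how many physicians enrolled saline women, how many women each contributed, and the estimated ICC for each symptom category.

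If the estimated ICC is near zero, the results will hardly move.

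The cost is slightly wider intervals and the loss of power shown in step 5. No new data collection is needed, but each questionnaire record must be linked to its site. The forms in Section 16.0 carry a site number, but they are the Amendment 2 reoperation and discontinuation forms. The documents do not show whether the questionnaire records carry one, so the sponsor should confirm the linkage first.

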**Table 2. CONTROLS**

Complication/ Condition/ Disease	Control
Local Complications	None needed
CTD	National norms 
Rheumatological Signs and Symptoms	Concurrent control group (saline breast implant patients)
Neurological Disease	National norms 
Neurological Signs and Symptoms	Concurrent control group (saline breast implant patients)
Offspring	National norms 
Reproductive	National norms 
Lactation	National norms 
Cancer	National norms 
Suicide	National norms 
Mammography	None needed
MRI Compliance and Results	None needed

 The sources for the comparison data will include Mayes et al. (2003) (Mayes, M., et al. 2003. Prevalence, incidence, survival, and disease characteristics of systemic sclerosis in a large US population. *Arthritis & Rheumatism* 48(8):2246-55), and may also include, as appropriate, relevant historical controls such as Brinton et al. (2004) (Brinton, L.A., et al. 2004. Risk of connective tissue disorders among breast implant patients. *Am. J. Epidemiol.* 160(7):619-27) and/or other reliable and relevant sources, including new sources that may become available during the course of this postapproval study. The sources for comparison data for fibromyalgia may include: Brinton et al. (2004), the saline implant concurrent controls, and/or other reliable and relevant sources, including new sources that may become available during the course of this postapproval study.

 The sources for the comparison data may include, as appropriate, relevant historical controls for each disease, such as Brinton et al. (2004) and Hennekens et al. (1996) (Hennekens, C.H., et al. 1996. Self-reported breast implants and connective-tissue diseases in female health professionals. A retrospective cohort study. *JAMA.* 275(8):616-21), and/or other reliable and relevant sources, including new sources that may become available during the course of this postapproval study.

 The sources for the comparison data may include, as appropriate, relevant historical controls such as the Centers for Disease Control's Pregnancy Risk Assessment Monitoring System (PRAMS), Center for Disease Control's Vital and Health Statistics, National Birth Defects Prevention Network, the California Birth Defects Monitoring Registry, the National Institutes of Health's (NIH's) First and Second Trimester Evaluation of Risk for Aneuploidy (FASTER) Trial, National Health and Nutrition Examination Survey (NHANES), and /or other reliable and relevant sources, including new sources that may become available during the course of this postapproval study, such as the National Children's Study.

 The sources for the comparison data may include, as appropriate, relevant historical controls such as Centers for Disease Control, National Survey of Family Growth, Centers for Disease Control Vital and Health Statistics, National Birth Defects Prevention Network, NIH's FASTER Trial, and/or other reliable and relevant sources, including new sources that may become available during the course of this postapproval study.

 The sources for the comparison data may include, as appropriate, relevant historical controls such as the CDC's Pregnancy Risk Assessment Monitoring System (PRAMS) and /or other reliable and relevant sources, including new sources that may become available during the course of this postapproval study.

 The sources for the comparison data may include, as appropriate, relevant historical controls such as Surveillance Epidemiology and End Results (SEER), Brinton et al. (2000, 2001) (Brinton, L.A., et al. 2000. Breast cancer following augmentation mammoplasty (United States). *Cancer Causes Control.* 11(9):819-27. *J. Long Term Eff. Med. Implants.* 12(4):271-9; Brinton, L.A., et al. 2001. Cancer risk at sites other than the breast following augmentation mammoplasty. *Ann. Epidemiol.* 11:248-56), Deapen et al. 1997 (Deapen, D.M., et al. 1997. Are breast implants anticarcinogenic? A 14-year follow-up of the Los Angeles study. *Plast. Reconstr. Surg.* 99:1346-1353), and /or other reliable and relevant sources, including new sources that may become available during the course of this postapproval study.

 The sources for the comparison data may include, as appropriate, relevant historical controls such as National Violent Death Reporting System, U.S. Census data (2002), Brinton et al. (2001, 2006) (Brinton,

*L.A., et al. 2001. Mortality among augmentation mammoplasty patients. Epidemiol. 12(3):321-6; Brinton, L.A., et al. 2006. Mortality rates among augmentation mammoplasty patients: an update. Epidemiol. 17(2):162-9) and/or other reliable and relevant sources, including new sources that may become available during the course of this postapproval study.*

